6.4.1. Exposure to the Drug

Duration of exposure will be calculated for each subject and summarized by treatment group.

For subjects without drug interruption, the duration of exposure for each subject is the date of last dose – date of first dose +1. If subjects have drug interruption, the duration of exposure for each subject is the (Treatment end date before drug interruption – date of first dose +1) + (date of last dose – treatment re-start date +1).

6.4.2. Adverse Events

Adverse events (AEs) will be classified by SOC and PT as defined by the MedDRA®.

A TEAE is defined as an event that first occurs or worsens in severity after baseline. The MedDRA Lowest Level Term (LLT) will be used in the treatment-emergent computation. The maximum severity for each LLT during the baseline period will be used as baseline. The Dosing Period will be included as postbaseline for the analysis. Events with a missing severity during the Dosing Period will be considered treatment-emergent. Events at baseline with missing severity and reports with severity change during the Dosing Period will be considered as treatment-emergent. For events occurring on the day of first taking study medication, the case report form (CRF)-collected flag will be used to determine whether the event was pre- versus post-treatment.

	Baseline	Postbaseline	Analysis
Part A			
Dosing Period	All pre-existing conditions recorded at Visit 1 and any AEs recorded before the first dose of study drug (during the interval between Visits 1 and 2 and recorded with the time of onset before the first dose of study drug)	Dosing period (during the interval between Visits 2 and 5)	All AE analyses
Follow-up	All AEs recorded during the last visit before discontinuing study drug.	Safety follow-up period (during the interval between Visits 5 and 801)	Only for post-exposure emergent AE by SOC and preferred term.
Part B			
Dosing Period	All pre-existing conditions recorded at Visit 101 and any AEs recorded before the first dose of study drug (during the interval between Visits 101 and 102 and recorded with the time of onset before the first dose of study drug)	Dosing period (during the interval between Visits 102 and 106)	All AE analyses
Follow-up	All AEs recorded during the last visit before discontinuing study drug.	Safety follow-up period (during the interval between Visits 106 and 802)	Only for post-exposure emergent AE by SOC and preferred term.
Long-term Extension			
Dosing Period	Any AEs recorded during the interval between Visits 105 and 106 and recorded with the time of onset before the first dose of study drug for the long-term extension.	Dosing period (during the interval between Visits 106 and 114)	All AE analyses
Follow-up	All AEs recorded during the last visit before discontinuing study drug.	Safety follow-up period (during the interval between Visits 114 and 805)	Only for post-exposure-emergent AE by SOC and preferred term.

For events that are sex specific, the denominator and computation of the percentage will only include subjects of the given sex. Otherwise, percentages will be calculated using the safety population as the denominator. Adverse events will be summarized as TEAEs.

In an overview table, the number and percentage of subjects who experienced a TEAE or serious adverse event (SAE), died due to an AE, or discontinued from study due to an AE will be summarized by treatment.

The frequency and percentages of subjects with TEAEs will be summarized by treatment using MedDRA PT nested within SOC. Events will be ordered by decreasing frequency within SOC. A common TEAEs (at least reported by 5% of subjects) summary will also be provided. As an additional table or figure, the percentages of subjects with TEAEs will be summarized by treatment using MedDRA PT (without regard to SOC). Events will be ordered by decreasing

frequency within PT. The frequency and percentages of subjects with TEAEs by maximum severity will also be summarized by treatment using MedDRA PT nested within SOC.

Fisher's exact test will be performed to compare percentages for each LY3337641 dose group and Placebo at both the SOC and PT levels.

Listings will be presented for all AEs, all SAEs, all AEs leading to death, all AEs leading to study drug temporary interruption, and all AEs leading to discontinuation from the study.

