6.2.5. Pre-existing Conditions and Medical History

Pre-existing Conditions and Medical History will be coded by Medical Dictionary for Regulatory Activities (MedDRA, most current available version). Data will be listed and summarized by treatment, system organ class (SOC), and preferred term (PT).

Pre-existing condition is defined as a condition with a start date on or before the informed consent date. Pre-existing conditions will be used to derive treatment-emergent adverse events (TEAEs) (Section 6.4.2).

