6.5.5. Analyses for the Optional Long-Term Extension Period

The objective of the optional long-term extension period is to collect long-term safety and efficacy data on LY3337641. For all subjects entering the long-term extension, the baseline visit is defined as Visit 106 in Part B.

Subjects will be grouped according to the treatment group in long-term extension and randomized treatment in Part B:

LY5mg(LTE)_Placebo(Part B); LY5mg(LTE)_LY5mg(Part B);

LY10mg(LTE)_Placebo(Part B); LY10mg(LTE)_LY10mg(Part B);
LY30mg(LTE)_Placebo(Part B); LY30mg(LTE)_LY30(Part B)

Unless otherwise specified, efficacy and health outcomes analyses will be conducted on the mITT population, defined as all randomized subjects receiving at least 1 dose of study drug. The analysis population (for applicable treatment outcome measures) will be all subjects with both a baseline and at least 1 postbaseline data measurement.

All variables and the change from baseline will be summarized by descriptive statistics. The statistics for continuous variables include mean, median, standard deviation, and number of observations. Categorical variables will be summarized by counts and percentages. No statistical hypothesis testing will be performed. The efficacy and health outcomes will be summarized as described in Section 6.3.

Safety analysis will be performed for all subjects entering the LTE, receiving at least 1 dose of the study drug and who do not discontinue the study for the reason “Lost to Follow-up” at the first postbaseline visit in LTE. The safety analysis will be conducted as described in Section 6.4. Duration of exposure will be calculated for each subject entering the LTE and summarized by treatment group for LTE period and cumulatively from Part B. Subjects who do not achieve response to study drug are eligible for rescue therapy at Week 16 and Week 20. From Week 24 onward, rescue therapy may be implemented for any subject determined to have ongoing active disease as assessed by the investigator. The safety, efficacy, and health outcome measures will be summarized separately for subjects who receive rescue therapies as described in Section 6.3 and Section 6.4.

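### The extension's adverse-event baseline looks back only to Visit 105 and omits pre-existing conditions, so some recurring complaints can be classed as emergent on LY3337641

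*SAP*

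**What the plan says.** SAP 6.4.2 gives the general rule: "A TEAE is defined as an event that first occurs or worsens in severity after baseline". It is applied term by term: "The maximum severity for each LLT during the baseline period will be used as baseline". A table in the same section then defines baseline and postbaseline for each study period.

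- **Part B dosing period.** The baseline is "All pre-existing conditions recorded at Visit 101 and any AEs recorded before the first dose of study drug". The Part A row is built the same way from Visit 1.
- **Long-term extension dosing period.** The baseline is "Any AEs recorded during the interval between Visits 105 and 106", limited to those that began before extension dosing started. Pre-existing conditions are not mentioned. The postbaseline period is "Dosing period (during the interval between Visits 106 and 114"), and the row applies to all AE analyses.

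Two other sections bear on this. SAP 6.2.5 states: "Pre-existing conditions will be used to derive treatment-emergent adverse events", and makes no exception for the extension. SAP 6.1.2 says that the safety baseline takes in all recorded pre-existing conditions, then refers to 6.4.2 for the definitions by period.

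SAP 6.5.5 sets the purpose: "The objective of the optional long-term extension period is to collect long-term safety and efficacy data on LY3337641". It sends extension safety to the methods of SAP 6.4, separates subjects by extension dose and by Part B arm, and plans no hypothesis testing. Under SAP 5.1, placebo subjects who enter are rerandomized 1:1:1 to the three doses at Week 12 and may receive LY3337641 for up to 52 weeks.

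**The concern.** The baseline row decides what counts as new. A term that is absent from the baseline window has no baseline severity, so a later report of it can be programmed as a first occurrence however often the subject had it before. The general wording about first occurrence does not prevent this, because first occurrence is judged after baseline and the row defines baseline.

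The placebo-to-LY3337641 groups are where this matters most. They are the extension's only view of newly started drug, and their first 12 weeks are drug-free history that could be used to recognize background complaints. The row discards the first eight of those weeks and the screening record. A background complaint could then appear in the treatment-emergent tables for a dose of LY3337641, including the treatment-emergent infection summaries of SAP 6.4.5.6.

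The same row applies to subjects who stay on LY3337641. An event of Weeks 0 to 8 that resolves and recurs can be counted as emergent in the Part B table and again in the extension table.

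**Working it through.** The plan states no figure on this point, so there is none to reproduce. The check sets the definitions side by side and adds simple arithmetic on visit days and group sizes.

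**Length of the look-back.** Inputs from the Part B Schedule of Activities (Protocol Appendix 2): Visit 102 = Day 1, Visit 105 = Day 57 ±3, Visit 106 = Day 85 ±3.

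- Extension baseline window: 85 − 57 = 28 days. With the visit tolerances: (85 − 3) − (57 + 3) = 22 days to (85 + 3) − (57 − 3) = 34 days.
- Part B dosing period: 85 − 1 = 84 days. Share inside the window: 28/84 = 33%.
- Share outside: (57 − 1)/84 = 56/84 = 67%. With tolerances: (54 − 1)/(88 − 1) = 61% to (60 − 1)/(82 − 1) = 73%.

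About the first two thirds of the placebo period, and the whole screening record, lie outside the extension baseline.

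**How the rule treats each kind of history.** Each case assumes a report in the extension at unchanged severity under the same LLT.

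| Earlier history of the term | In the extension baseline as written? | Class in the extension |
|---|---|---|
| On record at Visit 101, intermittent, no report in Weeks 8–12 | No | Can be emergent |
| AE only between Visits 102 and 105, resolved | No | Can be emergent |
| AE recorded between Visits 105 and 106, onset before first extension dose | Yes | Not emergent |
| AE that began before Visit 105 and is still ongoing | Not stated | Undetermined |
| Chronic condition, unchanged throughout | No | No new AE record expected (Protocol 8.2) |

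The last row follows from Protocol 8.2, under which sites record changes in existing conditions and new conditions as AEs. The exposed cases are therefore the first two rows. The second is the clearer, because the earlier event was itself recorded as an AE.

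**Conflict within the SAP.** The first row of the table would not be emergent under SAP 6.2.5 or the general sentence of SAP 6.1.2. It can be emergent under the extension row of 6.4.2. Because 6.1.2 defers to 6.4.2 for detail, a programmer working from the table would leave screening conditions out.

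**Weight of one subject.** SAP 5.2 plans 61 subjects per arm. Split 1:1:1, 61/3 = 20.3 placebo subjects per extension dose group at most. One misclassified subject is 1/20.3 = 4.9%, or about 5%, and more if fewer enter. SAP 6.4.2 uses 5% as its cutoff for common treatment-emergent events, so in groups this small a single subject can matter to what is displayed.

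**Number affected.** This would need the frequency of intermittent terms and their recurrence at unchanged severity. The documents give neither, so no estimate is offered.

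**The case against.** The strongest case on the other side has five parts.

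1. **The conflict may be only loose drafting.** SAP 6.1.2 and 6.2.5 both bring pre-existing conditions into the derivation, so the row need not be a decision to drop them. This stands as a reason to write that such terms *can* be counted. It does not settle the reading, because 6.1.2 hands the detail to the table that omits them.

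2. **The affected set is narrow.** A reader might infer that every pre-existing condition and every event first seen on placebo becomes emergent after the switch. The documents do not support that: placebo events between Visits 105 and 106 are in the baseline, unchanged chronic conditions should produce no AE record, and the handling of ongoing events is unstated. This stands.

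3. **The consequences are bounded.** Extension summaries are descriptive and switchers are shown separately. Serious AEs (SAP 6.4.2.1), discontinuations due to AEs (6.4.2.2), rash from its own form (6.4.5.2) and the listings of all AEs do not depend on the treatment-emergent label. The error over-counts and does not hide events. A reader might also infer that it spoils a comparison of extension with Part B rates. No such comparison is planned, and up to 52 weeks against 12 would make crude percentages hard to compare anyway. All this limits the weight of the point, but separate display does not correct a wrong label.

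4. **A short window has a purpose in continuing subjects.** Putting all Part B AEs into their extension baseline would absorb events that began on drug and hide their recurrence. This stands and shapes the fix. It gives no reason to discard placebo-period AEs in switchers, or screening conditions in anyone.

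5. **Protocol Addendum 1 governs the extension and was not available.** Its AE recording rules could not be checked. Even so, the SAP needs to agree with itself.

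**Conclusion.** The point holds in limited form. The extension row of SAP 6.4.2 is inconsistent with SAP 6.1.2 and 6.2.5, and its 28-day look-back allows a resolved or intermittent complaint from screening or Weeks 0 to 8 to be labelled emergent on LY3337641. It should be corrected before the extension is analyzed. Part A and Part B treatment-emergent results are untouched.

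The conclusion assumes that the table is programmed as written, that the recurrence is coded to the same LLT at no greater severity, and that the term is absent from the Visit 105 to 106 window. The ceiling of about 20 per switch group assumes that every placebo subject completes Part B and chooses to enter.

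**What to change.** Replace the extension baseline cell in SAP 6.4.2 with separate definitions for the two kinds of subject.

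- **Placebo-switch groups:** every condition on record at Visit 101, together with every AE that started before the first extension dose, at maximum severity per LLT.
- **Continuing LY3337641 groups:** keep the Visit 105 to 106 window for the extension-only table and add the pre-existing conditions. Also report a cumulative Part B plus extension table on the original Part B baseline. Do not move on-drug AEs of Weeks 0 to 8 into the extension-only baseline. In the cumulative table a subject whose event recurs is counted once for that term. It also matches the cumulative exposure that SAP 6.5.5 already plans.
- **Both:** state that events ongoing at Visit 105 belong to the baseline, and align SAP 6.1.2 and 6.2.5 with the revised row.

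The cost is a SAP edit, group-specific programming and one added table. Screening conditions and AEs by visit are already collected under Protocol Appendix 2. Treatment-emergent counts in the switch groups will be lower than under the present row.

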9.5.1. Adverse Events

Adverse events will be classified by system organ class and preferred term as defined by the *Medical Dictionary for Regulatory Drug Activities*. A TEAE is defined as an event that first

occurs or worsens in severity after baseline and on or prior to the date of the last visit within the dosing period. All pre-existing conditions recorded at Visit 1 (Part A) or Visit 101 (Part B) and any AEs recorded before the first dose of study drug (during the interval between Visits 1 and 2 for Part A or Visits 101 and 102 for Part B and recorded with the time of onset before the first dose of study drug) will be used as baseline. The dosing period will be included as the postbaseline period for analysis. For the Follow-Up Period, a follow-up-emergent adverse event is defined as an event that first occurs or worsens in severity after the last dose of study drug. For events that are sex specific, the denominator and computation of the percentage will only include subjects of the given sex.

Adverse events will be summarized as TEAEs. The frequency and percentage of TEAEs will be presented for each treatment group. All AEs, including pre-existing conditions, will be listed by subject, visit, preferred term, treatment group, severity, and relationship to the treatment.

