The optional long-term extension period will allow eligible subjects who complete Part B of Study JPDA to receive up to an additional 52 weeks of LY3337641. Subjects who complete the 12-week dosing period of Study JPDA Part B and who, in the opinion of the investigator, have no condition that would preclude continued participation in the study, will be eligible to participate in the extension. The last visit of the dosing period of Study JPDA Part B (Week 12, Part B) will also serve as the initial visit for the extension (Week 12, extension). Subjects who decide to participate in this addendum will not have the 2-week post-treatment safety follow-up period visit in Part B, but will enter the long-term extension period instead and have their 2-week safety follow-up visit at the end of the long-term extension period (Visit 805). Subjects will sign a separate informed consent form to enroll in the long-term extension period.

All subjects originally randomized to any dose of LY3337641 in Study JPDA Part B will continue on their current dose in the long-term extension. All subjects originally randomized to placebo in Study JPDA Part B will be rerandomized at the initial visit of the extension (Week 12) in a 1:1:1 ratio to receive 5, 10, or 30 mg of LY3337641. The entire long-term extension period will remain double-blind, as the dose of LY3337641 will remain blinded to the site and subjects. This addendum is considered unblinded to the sponsor once the main study is unblinded (see [Figure JPDA.5.2](#)).

Part A

[figure not shown]

Part B

Note: There will be an interim unblinded safety analysis by an assessment committee at least 2 weeks after all subjects have had their last dose in Part A. If a decision to proceed with the study is made, Part B will start enrolling new subjects. Part A subjects cannot participate in Part B.

Figure JPDA.5.1. Illustration of the study design for Clinical Protocol I8K-MC-JPDA.

*At Weeks 16 and 20, subjects who achieve at least a 20% improvement from baseline in either the tender or swollen joint count will be considered responders. Subjects who do not achieve response to study drug by this criterion will be eligible for rescue therapy. Starting at Week 24, rescue therapy may be implemented for any subject determined to have ongoing active disease as assessed by the investigator.

Figure JPDA.5.2. Illustration of the study design for optional long-term extension addendum of Clinical Protocol I8K-MC-JPDA(1).

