6.1.1. Analysis Population

Unless otherwise specified, efficacy and health outcomes analyses will be conducted on the modified intent-to-treat (mITT) population, defined as all randomized subjects receiving at least 1 dose of study drug. The analysis population (for applicable treatment outcome measures) will be all subjects with both a baseline and at least 1 postbaseline data measurement. Subjects will be grouped according to the randomized treatment. In addition, the primary analyses and key secondary efficacy analyses of Part B will be repeated using the per-protocol set (PPS), defined as all subjects randomly assigned to the study drug and using the study drug for 12 weeks without specified important protocol violations (Section [6.2.2](#)).

Safety analyses will be conducted on the safety population, defined as all randomized subjects receiving at least 1 dose of the study drug and who do not discontinue the study for the reason “Lost to Follow-up” at the first postbaseline visit. Subjects will be grouped according to the randomized treatment.

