6.4. Safety Analyses

All safety summaries and analyses will be based on the safety population as defined in Section 6.1.1. The safety population of the long-term extension (LTE) is defined in Section 6.5.5. Safety will be assessed by evaluating all reported AEs, AESIs, changes in vital signs, and changes in laboratory analytes.

Safety analyses will be conducted by randomized treatment for Part A and Part B separately. Follow-up Period will be summarized by the last used treatment in Part A or Part B. Subjects will be grouped according to the randomized treatment. If there are dose reductions during the study, key safety analyses will be grouped by the reduced dose treatment arm. P-values from statistical tests of treatment effects in safety analyses should be interpreted with caution as the analyses are intended to be descriptive and should not be considered as formal hypothesis testing. P-values and CIs, if reported, provide some evidence of the strength of the finding.

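### The Part B follow-up adverse-event percentages are taken over the whole safety population, including extension entrants who have no off-drug time in that window, so the shown rate is the true rate times one minus the share entering the extension

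*SAP*

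**What the plan says.** **Population and denominator.** SAP 6.4 opens with "All safety summaries and analyses will be based on the safety population as defined in Section 6.1.1". SAP 6.1.1 defines that population: "Safety analyses will be conducted on the safety population, defined as all randomized subjects receiving at least 1 dose of the study drug". It then removes subjects lost to follow-up at the first postbaseline visit, but sets no condition on having an off-drug period. SAP 6.4.2 adds the rule for percentages: sex-specific events use subjects of that sex, and "Otherwise, percentages will be calculated using the safety population as the denominator".

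**The follow-up table.** For Part B, the period table in SAP 6.4.2 defines the follow-up window as "Safety follow-up period (during the interval between Visits 106 and 802" and assigns it one analysis, post-exposure emergent events by system organ class and preferred term. On grouping, SAP 6.4 says "Follow-up Period will be summarized by the last used treatment in Part A or Part B".

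**Extension entrants.** SAP 5.1 states: "Subjects who decide to participate in this addendum will not have the 2-week post-treatment safety follow-up period visit in Part B". They go straight into the extension, with placebo subjects rerandomized to one of the three active doses. The period table gives their time from Visit 106 to the extension: "Dosing period (during the interval between Visits 106 and 114". Their off-drug window comes only afterwards, between Visits 114 and 805.

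**What counts as a follow-up event.** Protocol 9.5.1 says "a follow-up-emergent adverse event is defined as an event that first occurs or worsens in severity after the last dose of study drug".

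**The concern.** Read together, these rules keep extension entrants in the denominator of a table to whose numerator they cannot contribute. They have not taken a last dose at Visit 106, and the SAP counts their subsequent time as extension dosing. A placebo subject who moves to active drug would sit in the placebo follow-up denominator as event-free.

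The drug is an irreversible inhibitor (Protocol 2.1), so events after stopping are of real interest, and this is the planned percentage table for the Part B off-drug window. Any extension entry lowers the shown percentage. Entry is optional and open only to Part B completers whom the investigator judges fit to continue, so the share entering may differ between arms, and the dilution would then differ too.

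It looks like an oversight. The SAP revision history shows that the extension analyses were added in Version 2. SAP 6.5.5 restricts the extension safety analysis to subjects who enter the extension, but no matching restriction was made for Part B follow-up.

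**Working it through.** **Inputs**
- Arm size: 61 (Protocol 9.1, SAP 5.2), used here as the size of an arm's safety population. The actual number may be slightly lower under SAP 6.1.1.
- Denominator rule, window and extension flow: as set out above.
- Share of an arm entering the extension, u: not in either document, so an assumption throughout. The completion rate is not given either.

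**1. The plan's own figure.** For 30% versus 55%, two-sided .05, 80% power, pooled variance under the null and no continuity correction:

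n = [1.960 × √(2 × 0.425 × 0.575) + 0.842 × √(0.30 × 0.70 + 0.55 × 0.45)]² / 0.25² = 60.2, rounded up to 61 per arm (power 80.5%).

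The stated size reproduces. It serves here only as the arm size.

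**2. Effect of the denominator.** Let N be the arm's safety population, u the share entering the extension and p the true risk among those off drug. Suppose every non-entrant is observed after the last dose.
- Expected events = p × N × (1 − u)
- Shown rate = p × N × (1 − u) / N = p × (1 − u)
- Understatement factor = 1 / (1 − u)

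| u (assumed) | Enter, of 61 | Not entering | Factor 1/(1 − u) | True 10% shown as | 3 events over 61 | 3 events over those not entering |
|---|---|---|---|---|---|---|
| 10% | 6 | 55 | 1.1 | 9.0% | 4.9% | 5.5% |
| 25% | 15 | 46 | 1.3 | 7.5% | 4.9% | 6.5% |
| 50% | 30 | 31 | 2.0 | 5.0% | 4.9% | 9.7% |
| 67% | 41 | 20 | 3.0 | 3.3% | 4.9% | 15.0% |
| 80% | 49 | 12 | 5.0 | 2.0% | 4.9% | 25.0% |

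**3. What a given factor requires.** Only completers can enter, so u = c × f, with c the completion rate and f the uptake among completers. A 3-fold factor needs u = 0.667. That is f = 0.667/0.90 = 74% at 90% completion, or 0.667/0.80 = 83% at 80% completion. At 90% completion and 25% uptake the factor is 1/(1 − 0.225) = 1.29.

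**4. Unequal entry.** With a true 10% in both arms and u of 60% and 80%, the table would show 10% × 0.40 = 4.0% and 10% × 0.20 = 2.0%. The apparent twofold difference comes from the denominator alone.

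Part A follow-up is unaffected, because only Part B completers can enter the extension.

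**The case against.** **The rule may not be meant for this table.** The sentence after the denominator rule in SAP 6.4.2 says that adverse events are summarized as TEAEs, and the percentage tables described next are of treatment-emergent events. The rule could therefore be read as covering dosing-period tables only, and grouping follow-up by last used treatment might imply subjects who actually have a follow-up period. This does not remove the problem. SAP 6.4 places all safety summaries on the safety population, follow-up included. Even without that, the follow-up table would have no stated denominator, and the same sentence would be needed.

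**The size is unknown.** A reader might infer that rates are understated several-fold. The documents do not support that as a general statement. They give neither uptake nor completion, and at 25% entry the factor is 1.3.

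**Off-drug events are not hidden.** A reader might infer that this table is the only off-drug safety output for Part B. It is not. SAP 6.4.2 also plans listings of all adverse events and all serious events. The registry analysis in SAP 6.5.4 counts serious events whether or not they are treatment-emergent, and both documents plan HBV DNA analyses after the last dose. The event counts in the follow-up table are correct under either denominator; only the percentages are wrong.

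**Consequences are limited.** The SAP treats safety p-values as descriptive, and no efficacy endpoint depends on this table. That stands, and it bounds the importance of the point.

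**Removing entrants does not restore a randomized comparison.** This also stands. If subjects with adverse events tend to decline the extension, the non-entrants in each arm are a group selected after randomization.

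**Conclusion.** The concern holds for the percentages in one table. As written, SAP 6.4 and 6.4.2 divide Part B post-exposure events by a population that includes subjects with no off-drug time in the window. The direction follows from the text: any entry into the extension lowers the shown rate, by the factor (1 − u). The size does not follow from the text. It is 1.3-fold at u = 25% and 5-fold at 80%, and u is an assumption across that range. The formula also assumes that every non-entrant is observed after the last dose; if some are not, the understatement is larger. Unequal entry can distort the comparison between arms as well, and a better denominator removes the dilution but not the selection. This should be corrected before the Part B final analysis. It does not put the primary analysis in doubt.

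**What to change.** Add to SAP 6.4.2 a denominator for the Part B follow-up table: safety-population subjects who stopped study drug, did not enter the long-term extension and have observation after the last dose, grouped by last used treatment. The observation condition is needed because some early discontinuers may have none: they may be lost to follow-up, and the schedule of activities requires Visit 802 of them only if the early discontinuation visit falls less than 2 weeks after the last dose.

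Print that N and the number entering the extension for each arm. Label comparisons between arms in this table as descriptive, since non-entrants are selected after randomization.

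The cost is a sentence in the SAP and one population flag, with no change to conduct or data collection. The downside is smaller denominators and less precise percentages: with 12 subjects left in an arm, one event moves the rate by 1/12 = 8.3 percentage points, against 1/61 = 1.6 now.
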